**5.1.1 Dose Modification for hematologic toxicities after cycle 1 (for Phase 1) and during allcycles (for Phase 2):**

If the ANC is less than 500/ $\mu$ L or the platelet count is less than 30,000/ $\mu$ L, then the study drug may be held for up to 8 weeks. Study drug may be re-instituted at the next lower level (i.e. from 15mg to 10 mg) if ANC is  $\geq$  500/  $\mu$ L or the platelet count is  $\geq$  30,000/ $\mu$ L. If however, after an 8 week treatment delay, the ANC remains <500/ $\mu$ L or the platelet count <30,000/  $\mu$ L, the patient will be removed from protocol therapy.

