In Phase 2, patients will receive the lenalidomide dose recommended in the Phase 1 portion. 30 patients will be enrolled in Phase 2. Study procedures are the same as the Phase 1 portion. Subjects will be able to continue the study treatment until disease progression or unacceptable toxicity. Detailed discontinuation information is provided in Section 5.4.

A new course of treatment may begin on the scheduled day 1 of a new cycle if;

- Absolute neutrophil count  $\geq 1,000$  / mL
- Platelets count  $\geq 50,000$
- Resolution of adverse events to  $\leq$  grade 1 (Details in Section 5.1).

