**5.1.2 Dose Modification for Non-Hematologic Toxicities after cycle 1 (for Phase 1) and during all cycles (for Phase 2):**

*Neurologic Toxicity*

If a patient experiences  $\geq$  3 neurologic toxicity, then the study drug may be held for as many as 8 weeks. If toxicity resolves to  $\leq$  1, then the study drug may be reinstated at the next lower dose. If, however, after an 8 week treatment delay, the toxicity does not resolve to  $\leq$  1 the patient will be removed from protocol therapy.

*Cardiac Toxicity*

If a patient experiences  $\geq$  2 cardiac toxicity, then the study drug may be held for as many

as 8 weeks. If toxicity resolves to  $\leq 1$ , then the study drug may be reinstated at the next lower dose. If, however, after an 8 week treatment delay, the toxicity does not resolve to  $\leq 1$  the patient will be removed from protocol therapy.

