## 5.2 Concomitant Medications

No investigational or commercial agents or therapies other than those described below may be administered with the intent to treat the patient's malignancy.

Participants who receive radiation therapy or chemotherapy after transplantation are considered to have treatment failure, unless the radiation was pre-planned consolidation and that decision was made before transplantation.

Any other treatments (including drugs, biological products, and blood products) the patient is receiving at the time of screening or has received within one to four weeks prior to registration and during therapy should be recorded on the concomitant medications page of the case report forms (CRFs). Use of colony stimulating factors (G-CSF or GM-CSF) and Erythropoietin are prohibited during the study. Subjects who need colony stimulating factors or erythropoietin should be taken off from the study.

All concomitant medications and supportive therapy received during study treatment must be recorded.

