## 5.3 Supportive Care

Prophylactic aspirin or low molecular weight heparin are to be given to all patients receiving lenalidomide (as DVT prophylaxis) unless contraindicated. Prophylactic blood product support is discouraged however blood product transfusions are allowed for symptomatic patients who have clinically significant anemia or thrombocytopenia.

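### Section 5.1.1 joins the two blood-count restart conditions with 'or', so read literally drug may be restarted within a cycle while one count is still below its hold limit

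*Combined protocol and SAP*

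**What the plan says.** Section 5.1.1 applies after cycle 1 in Phase 1 and in all cycles of Phase 2. It contains three rules on the same two counts.

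- **Hold.** If the ANC is below 500/µL or platelets are below 30,000/µL, "then the study drug may be held for up to 8 weeks".
- **Restart.** "Study drug may be re-instituted at the next lower level (i.e. from 15mg to 10 mg) if ANC is" at least 500/µL or the platelet count is at least 30,000/µL.
- **Removal.** "If however, after an 8 week treatment delay, the ANC remains" below 500/µL or platelets remain below 30,000/µL, the patient comes off protocol therapy.

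Two other places bear on how the restart sentence is read. In Section 5.1.2, the neurologic and cardiac rules allow restart once toxicity is grade 1 or less. They require removal on the opposite condition: "If, however, after an 8 week treatment delay, the toxicity does not resolve to" grade 1 or less. In Section 5, a separate list governs the start of a cycle: "A new course of treatment may begin on the scheduled day 1 of a new cycle if" the ANC is at least 1,000, platelets are at least 50,000 and adverse events have resolved to grade 1 or less. Section 5.1.1 does not refer to that list.

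**The concern.** 'Or' is right in the hold and removal sentences, where one low count is enough to act. The opposite of 'either count is low' is 'both counts have recovered', so the restart sentence needs 'and'. As written, a patient with a single low count qualifies for the hold and for the restart at the same moment.

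What is at stake is safety. Patients are aged 60 to 80 and have had a transplant, and Table 5 in Section 9.8 treats myelosuppression from lenalidomide as expected. Growth factors are not available as a rescue within the study: "Subjects who need colony stimulating factors or erythropoietin should be taken off from the study" (Section 5.2). Section 5.3 states "Prophylactic aspirin or low molecular weight heparin are to be given to all patients receiving lenalidomide (as DVT prophylaxis) unless contraindicated", and also "Prophylactic blood product support is discouraged", although transfusion is allowed for symptomatic patients. Restarting drug at platelets of 15,000/µL in that setting could add bleeding risk. Restarting at an ANC of 200/µL would expose a patient who is already severely neutropenic to a myelosuppressive drug.

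**Working it through.** No sample-size, power or error-rate figure is involved, and the plan states no number to reproduce. The check is whether the three rules are consistent with one another.

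**Inputs (Section 5.1.1).** Let A mean ANC below 500/µL and P mean platelets below 30,000/µL.

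- Hold: A or P.
- Removal after 8 weeks: A or P (the same condition).
- Restart as written: not A, or not P. This equals 'not both low'.
- Restart with 'and': not A, and not P. This equals 'not (A or P)', the exact complement of the hold and removal conditions.

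**All four states.**

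| ANC | Platelets | Hold | Restart as written | Restart with 'and' | Removal if still so at 8 weeks |
|---|---|---|---|---|---|
| ≥500 | ≥30,000 | no | yes | yes | no |
| ≥500 | <30,000 | yes | **yes** | no | yes |
| <500 | ≥30,000 | yes | **yes** | no | yes |
| <500 | <30,000 | yes | no | no | yes |

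Three states trigger a hold. As written, 2 of these 3 also meet the restart condition, and the same 2 meet both restart and removal at week 8. With 'and', the overlap is 0 of 3.

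**Two worked cases.**

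- Platelets 15,000/µL, ANC 1,200/µL: held, because 15,000 < 30,000. Restart as written is met, because 1,200 ≥ 500. Restart with 'and' is not met.
- ANC 200/µL, platelets 100,000/µL: held, because 200 < 500. Restart as written is met, because 100,000 ≥ 30,000. Restart with 'and' is not met.

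**Does another section close the gap?** The Section 5 day-1 limits are higher than the hold limits (1,000 against 500; 50,000 against 30,000). Any patient with one count below its hold limit therefore fails them, so a restart on scheduled day 1 of a new cycle is blocked. For a restart inside a cycle only Section 5.1.1 speaks.

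**What was intended?** The removal sentence takes a patient off therapy when either count is still low, so staying on therapy requires both to recover. The neurologic and cardiac rules in Section 5.1.2 are built as exact opposites. Only the restart sentence in 5.1.1 breaks that pattern.

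**The case against.** The best defence is that the restart sentence mirrors the hold sentence and can be read in pairs: restart when the count that caused the hold has recovered. On that reading neither worked case qualifies. The reading is possible, but the text does not state it. It would also still permit restart when the triggering count has recovered and the other has since fallen below its limit.

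Several further points stand and limit the severity.

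- The language is permissive. Drug may be held and may be restarted, and only removal is mandatory. At week 8 the mandatory rule would prevail, so the overlap there is an inconsistency and not a deadlock.
- From cycle 3, scheduled visits and blood counts occur once per cycle, in week 1 (Section 6.2), close to the point where the day-1 limits apply. The window in which the faulty sentence would operate is therefore narrow. The same schedule also means that a mid-cycle restart may have no scheduled count until the next cycle.
- The aspirin and heparin instruction carries an exception for contraindication. Section 5.4 lets the investigator withdraw a patient for a laboratory abnormality, and Section 11.1 has the principal investigator and the monitoring committee reviewing toxicity.

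A reader might infer that the protocol directs sites to redose patients with severe cytopenia. The documents do not support that: the sentence permits and does not instruct, and its neighbour points the other way.

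**Conclusion.** The concern holds as a drafting error with a patient-safety consequence, and it should be corrected. Read literally, Section 5.1.1 allows restart within a cycle in 2 of the 3 states that trigger a hold; with 'and' it allows restart in none of them.

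This rests on the literal text and on the day-1 criteria in Section 5 applying only where they say they do, at the start of a cycle. If the sponsor intended them to govern every restart, the gap would close, but Section 5.1.1 does not say so and sets lower limits of its own.

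Two larger conclusions are tempting and should be resisted. First, '2 of 3' counts rule states, not patients. The documents give no frequency for these count combinations, so no number of affected patients can be derived. A careful physician would probably require both counts in any case. Second, the error does not reach the trial's conclusions. DLT and MTD are decided in cycle 1 of Phase 1, where this rule does not apply, and the two-year relapse-free survival estimate and test in Section 10.1 do not use it.

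**What to change.** Replace the restart sentence in Section 5.1.1 with wording to this effect: *Resumption at the next lower dose level is permitted only when the ANC is at least 500/µL AND the platelet count is at least 30,000/µL.*

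Leave the hold limits, the 8-week removal rule and the Section 5 new-cycle criteria unchanged. The day-1 limits should not be copied into this sentence: on day 1 that would be redundant, and elsewhere it would raise the restart thresholds.

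The cost is one changed conjunction. A patient with one count still low waits longer to restart, within the existing 8 weeks. Thresholds, DLT rules, sample size and analysis are untouched.

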**5.1.2 Dose Modification for Non-Hematologic Toxicities after cycle 1 (for Phase 1) and during all cycles (for Phase 2):**

*Neurologic Toxicity*

If a patient experiences  $\geq$  3 neurologic toxicity, then the study drug may be held for as many as 8 weeks. If toxicity resolves to  $\leq$  1, then the study drug may be reinstated at the next lower dose. If, however, after an 8 week treatment delay, the toxicity does not resolve to  $\leq$  1 the patient will be removed from protocol therapy.

*Cardiac Toxicity*

If a patient experiences  $\geq$  2 cardiac toxicity, then the study drug may be held for as many

as 8 weeks. If toxicity resolves to  $\leq 1$ , then the study drug may be reinstated at the next lower dose. If, however, after an 8 week treatment delay, the toxicity does not resolve to  $\leq 1$  the patient will be removed from protocol therapy.

#### *Venous Thrombosis*

Patients who develop signs or symptoms suggestive of thrombosis should be evaluated and treated as clinically indicated. Lenalidomide should be held for patients with venous thrombosis. Lenalidomide may resume when patient are adequately anti-coagulated. Patients with recurrent thrombosis despite adequate anticoagulation should be removed from protocol therapy.

#### *Renal Toxicity*

For creatinine clearance (CrCl)  $< 30$  mL/min skip lenalidomide and reassess in four weeks. If CrCl remains  $< 30$  mL/min after four weeks, then protocol therapy should be terminated.

For CrCl  $< 60$  mL/min but  $\geq 30$  mL/min:

Decrease lenalidomide to next lower dose level. Reassess after four weeks and attempt to re-escalate lenalidomide.

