### **3. PATIENT SELECTION**

#### **3.1 Inclusion Criteria**

- 3.1.1. Patients must have a Confirmed diagnosis of non-M3 AML. Antecedent MDS is acceptable.
- 3.1.2. Post autologous Stem Cell Transplant Bone marrow biopsy core that is consistent with morphologic remission.
- 3.1.3. Age between 60 and 80years old.
- 3.1.4. Must have received induction and consolidation chemotherapy, and autologous stem cell transplant for AML.
- 3.1.5. Life expectancy of greater than 12 months.
- 3.1.6. Karnofsky Performance Status 70 or greater (see Appendix A)
- 3.1.7. Patients must have normal organ and marrow function as defined below:
  - Leukocytes  $\geq 2,000/\text{mCL}$
  - Absolute neutrophil count  $\geq 1,000/\text{mCL}$
  - Platelets  $\geq 75,000/\text{mCL}$
  - Total bilirubin  $\leq 4 \times$  institutional upper limit of normal unless 2nd to Gilbert's disease
  - AST(SGOT) and ALT(SGPT)  $\leq 4 \times$  institutional upper limit of normal
  - Creatinine  $< 1.5 \times$  institutional upper limit of normal OR creatinine clearance  $\geq 30 \text{ mL}/\text{min}/1.73 \text{ m}^2$  for patients with creatinine levels above institutional normal.
- 3.1.8 Able to take aspirin, or warfarin, or low molecular weight heparin as prophylactic anticoagulation.
- 3.1.9. Ability to understand and the willingness to sign a written informed consent document.
- 3.1.10 Must be registered into the mandatory RevAssist® program and be willing and able to comply with the requirement of RevAssist®.

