1 out of 3	Recruit at least three more patients at this dose level. 
 
• If none of these patients experience with DLT, proceed to the next higher dose level
 
• If one or more of this group suffer DLT, then dose escalation is stopped and this dose is declared MTD. Three additional patients will be entered at the next lower dose level if only three patients were treated previously at that dose.
 

≤ 1 out of 6 at highest dose level below the MTD	This will be the recommended Phase 2 dose. At least six patients must be recruited at the recommended Phase 2 dose.

If no DLT is observed at the final 25 mg dose level in the first three patients, three additional patients at the 25 mg dose level will be recruited. In Phase 1, in order to declare Therapeutic Dose Level (TDL), a minimum of six patients must be recruited at that dose level. Therapeutic

Dose Level (TDL) is defined as the dose level where DLT occurred in less or equal to one out of six patients below the Maximally Tolerated Dose level. TDL will be the recommended dose for Phase 2.

If a DLT is observed in two or more patients at the first dose level (10 mg), then dose level -1 (5 mg) will be tested with three patients first. Three additional patients will be enrolled at the 5 mg dose, if one or less DLT is observed. If one or more of this group suffers DLT, then the study is stopped and lenalidomide maintenance for elderly AML patients post autologous transplant is not deemed feasible (same as if  $\geq 2$  had a DLT to initial cohort of 5 mg).

Decisions about DLTs, expansion of a cohort to six subjects, escalation to the next dose level, or reduction to the next lower level will be made by Principle Investigator.

In Phase 1, subjects will continue study drug, lenalidomide until disease progression or unacceptable toxicity. Reported adverse events and potential risks for lenalidomide are described in Section 2.5. Dose modifications are described in Sections 5.1 and in Table 3. Subjects who are withdrawn without a DLT before completing Cycle 1 will not be used to evaluate the MTD or TDL, but will be included in the overall safety analysis.

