### **5.1 Dose modifications**

At Phase 1, subjects who develop any DLT during cycle 1 will be taken off the study. During cycle 2 and onward, dose reductions are allowed. Dose reduction rules are the same for subjects enrolled in Phase 2 (Table 3). Reduced doses will not be re-escalated for any subject during the study. Subjects may not continue Lenalidomide after the third dose reduction or beyond dose of 2.5 mg.

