## 6.2. Treatment Period

### Cycle 1 - Day 1 (Week 1) visit:

All assessments must be completed prior to dosing with Lenalidomide. If Cycle 1 Day 1 date is no more than three days from screening laboratory assessments, then labs performed during screening may be used.

Assessments required for Cycle 1 Day 1:

- Physical Examination
- Karnofsky performance status
- Vital signs (blood pressure, heart rate and temperature)
- Complete Blood counts with differential and serum chemistries (see Appendix D for details).
- Concomitant medications assessment
- Adverse events assessment
- Start of Lenalidomide treatment

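### Renal dosing rules do not fit together: 5.1 and 5.1.2 conflict on re-escalation, and eligibility can admit a CrCl below the 5.1.2 stop level, which is not enforced in Phase 1 cycle 1

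*Combined protocol and SAP*

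**What the plan says.** **Re-escalation.** Section 5.1 states: "Reduced doses will not be re-escalated for any subject during the study". The renal paragraph of 5.1.2 steps the dose down one level for a CrCl from 30 to below 60 mL/min and then says: "Reassess after four weeks and attempt to re-escalate lenalidomide". No renal exception to the 5.1 rule is written.

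**Entry.** Criterion 3.1.7 accepts creatinine below 1.5 times the "institutional upper limit of normal OR creatinine clearance" of at least 30 mL/min/1.73 m², with the clearance part attached to patients whose creatinine is above normal. Form 1 (Appendix B) repeats the line.

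**Stop level.** Under 5.1.2, a CrCl below 30 means the drug is skipped and CrCl is reassessed in four weeks. If it is still below 30 "mL/min after four weeks, then protocol therapy should be terminated".

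**Scope.** The heading of 5.1.2 reads "Dose Modification for Non-Hematologic Toxicities after cycle 1 (for Phase 1) and during all cycles (for Phase 2". For Phase 1 cycle 1, 5.1 provides only removal for a dose-limiting toxicity (DLT); dose reductions start in cycle 2. Section 5.4 separately lets the investigator withdraw a subject for a laboratory abnormality.

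**Evaluability.** Section 5 says: "Subjects who are withdrawn without a DLT before completing Cycle 1 will not be used to evaluate the MTD or TDL". It does not say that such subjects are replaced.

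**The concern.** The first issue is a direct conflict between two instructions. After a passing fall in CrCl, a site following 5.1 keeps the patient on the reduced dose for good, while a site following 5.1.2 takes the dose back up. The renal paragraph also names no CrCl value that permits the step up.

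The second issue is patient safety. Section 2.5 reports that about two-thirds of the drug leaves unchanged in the urine in healthy volunteers, and the protocol itself withholds dosing below 30 mL/min. If entry does not guarantee at least 30, someone can be registered at a clearance where the drug should not be given. In Phase 2 the skip rule catches that patient at once. In Phase 1 cycle 1, the cycle on which dose escalation is decided, no CrCl-based hold is written.

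**Working it through.** The plan gives no figure on this point to reproduce. The check uses its own rules and formula.

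**Inputs from the protocol:** age 60 to 80 (3.1.3); creatinine limit 1.5 × ULN (3.1.7); CrCl threshold 30 mL/min (5.1.2); dose steps (Table 3); 8 patients a year (10.2); Cockcroft-Gault (Appendix E): CrCl = (140 − age) × kg / (72 × creatinine), times 0.85 for women.

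**Assumed:** ULN 1.0 to 1.2 mg/dL; example weights of 50 to 70 kg; Appendix E as the method for both 3.1.7 and 5.1.2. It is the only method given, but neither section cites it.

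**Step 1, re-escalation.** After one renal step-down (Table 3):

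| Dose before | Following 5.1 | Following 5.1.2, if re-escalated | Size of step |
|---|---|---|---|
| 25 mg | 15 mg | 25 mg | 1 − 15/25 = 40% |
| 15 mg | 10 mg | 15 mg | 1 − 10/15 = 33% |
| 10 mg | 5 mg | 10 mg | 1 − 5/10 = 50% |

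**Step 2, creatinine at which CrCl is 30.** Creatinine = (140 − age) × kg × (0.85 for women) / (72 × 30). The patient passes the creatinine limit with CrCl below 30 when ULN exceeds that value divided by 1.5.

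| Patient | Creatinine at CrCl 30 (mg/dL) | ULN must exceed |
|---|---|---|
| Woman 80 y, 50 kg | 60 × 50 × 0.85 / 2160 = 1.18 | 0.79 |
| Woman 80 y, 60 kg | 60 × 60 × 0.85 / 2160 = 1.42 | 0.94 |
| Woman 75 y, 60 kg | 65 × 60 × 0.85 / 2160 = 1.53 | 1.02 |
| Man 80 y, 60 kg | 60 × 60 / 2160 = 1.67 | 1.11 |
| Man 80 y, 70 kg | 60 × 70 / 2160 = 1.94 | 1.30 (outside the assumed range) |

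**Step 3, lowest CrCl admitted on creatinine alone.** Just under the limit, creatinine is 1.49 (ULN 1.0) or 1.79 (ULN 1.2).

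- Woman 80 y, 60 kg: 3060 / (72 × 1.49) = 28.5; 3060 / (72 × 1.79) = 23.7.
- Woman 80 y, 50 kg: 2550 / (72 × 1.49) = 23.8; 2550 / (72 × 1.79) = 19.8.

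**Step 4, stricter reading of 3.1.7.** Suppose anyone above normal creatinine must show a CrCl of at least 30. The gap then remains only for creatinine up to ULN. For a woman of 80, CrCl is below 30 at ULN when weight is below 30 × 72 × ULN / (60 × 0.85), which is 42.4 kg at ULN 1.0 and 50.8 kg at ULN 1.2. For a man of 80, without the 0.85, the limits are 36.0 and 43.2 kg.

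**Step 5, what the text does with such a patient.**

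- Phase 2, any cycle, and Phase 1 from cycle 2: skip, reassess at four weeks, terminate if still below 30.
- Phase 1 cycle 1: 5.1.2 is out of scope. A low CrCl already present at entry is not a drug-related grade 3 or 4 event, so it is not a DLT. What remains is discretionary withdrawal under 5.4.

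**The case against.** The best counter-argument concerns 3.1.7. If creatinine below 1.5 × ULN is enough alone, limiting the clearance part to patients above normal does no work, because anyone at or over 1.5 × ULN is above normal already. That favours the stricter reading and shrinks the entry gap to the very light patients of step 4. This stands as a limit on size. The literal OR is still there, though, and Form 1 repeats it, so central registration does not resolve it.

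On re-escalation, the renal sentence can be read as a specific exception that follows a reassessment of CrCl. But 5.1 covers any subject, and no exception or threshold is written.

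Several stronger readings are tempting and are not supported:

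- *A Phase 1 patient below 30 is bound to receive a full cycle.* The cycle 1 day 1 visit says "All assessments must be completed prior to dosing with Lenalidomide", chemistries are repeated weekly in that cycle, registration follows discussion with the principal investigator, and 5.4 permits withdrawal. A low value would be seen; what is missing is a rule.
- *The new-cycle conditions prove the gap.* The list after "A new course of treatment may begin on the scheduled day 1 of a new cycle if" omits CrCl, but from cycle 2 the 5.1.2 skip rule already covers this.
- *The indexed unit in 3.1.7 is a second route in.* An indexed 30 would be 30 × 1.5 / 1.73 = 26.0 mL/min at an assumed body surface area of 1.5 m². But Appendix E returns plain mL/min, so the indexing may be a slip of units.
- *Stable patients entering at 30 to 59 must be cut on day 1 of Phase 2.* The Renal Toxicity heading and the talk of re-escalating favour a fall during treatment.
- *The two-year result or the power is distorted.* The documents give no frequency from which to show that.

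**Conclusion.** The plan is wrong as written on two linked points, both minor.

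1. Sections 5.1 and 5.1.2 contradict each other on re-escalation after a renal reduction. This rests on the text alone; the dose in dispute differs by one Table 3 level.
2. Entry does not guarantee the clearance at which 5.1.2 allows dosing. Read literally, 3.1.7 can admit a woman of 80 years and 60 kg at a CrCl of about 28 (ULN 1.0) or 24 (ULN 1.2). Read strictly, it leaves very light elderly patients, chiefly women of 80 under about 42 to 51 kg. In Phase 1 cycle 1 the only written responses are removal for a DLT and discretionary withdrawal.

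The second point rests on assumed ULN and weights and on Appendix E being the intended method. Termination follows only if CrCl is still below 30 at four weeks. How many patients would be affected cannot be computed from the documents; entry below 30 is likely rare. The point concerns safety and consistent dosing, with no effect on efficacy or power claimed.

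**What to change.** 1. **Re-escalation.** In 5.1, exempt renal reductions from the ban. In 5.1.2, allow one level up only if CrCl is 60 mL/min or more at the four-week reassessment; otherwise the dose stays. The alternative is to delete the re-escalation sentence in 5.1.2.
2. **Entry.** In 3.1.7 and Form 1, replace the creatinine line with a Cockcroft-Gault CrCl (Appendix E, mL/min, not indexed) of at least 30 for all patients.
3. **Skip rule.** Apply the rule for CrCl below 30 in every cycle of both phases. In Phase 1 cycle 1, count the event as a DLT if it meets the 5.1 definition. Otherwise state that the patient is not evaluable for the maximum tolerated or therapeutic dose level and is replaced. This needs a new sentence: the existing one covers only withdrawals, and a skipped course is not a withdrawal.

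**Cost.** Wording only in 3.1.7, Form 1, 5, 5.1 and 5.1.2. Weight and creatinine are already collected at screening, so there are no new tests. A few patients below 30 are excluded. If 3.1.7 really meant the indexed value, a few patients with a body surface area above 1.73 m² could newly qualify. Each replaced Phase 1 patient costs about 12 / 8 = 1.5 months at the planned accrual.
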